- e Local thick and thin blood films performed at the site, before Informed Consent signature, according to local standard procedures and within 4 hours prior to dosing, can be used as screening/ pre-dose parasitemia assessments (Section 9.1.1.1) provided that a standard procedure is in place at site and blood films staining is performed according to the study operational manual. Blood films (thick and thin) and temperature measurements need to be confirmed as follows: when 1st parasite clearance and 1st temperature < 37.5 °C, measurements need to be confirmed with second reading 6 to 12 hours after the first measurement (ie, to determine Parasite Clearance and Fever Clearance). The first measurement (if confirmed) will be considered the 'Clearance Time'. Asexual and sexual counts will be measured separately: only asexual count will be used as parasitemia for evaluation of study endpoints. If parasites have not cleared within 72 hours after IMP administration and criteria for rescue medication are not met at 72 hours post-dose, blood films should continue to be taken according to site standard practice (or at minimum every 8 hours) until parasite clearance is shown or until criteria for rescue medication are met (see Section 7.7.1). If these additional blood smears are taken they should be recorded as unscheduled visits in the e-CRF. Axillary temperature should be recorded, if the axillary method is not possible, an alternative route (oral, tympanic, rectal) may be used. Within an individual participant the same method of temperature measure should be used throughout the study.
- f RT-qPCR and qPCR will be performed at all parasitemia time-points (To be collected, according to the schedule and the instructions reported in the study operational manual). Parasite genotyping analysis will be performed on previously collected blood spot sample only in case of a positive blood film after initial parasite clearance: one pre-dose sample and one sample at 18 or 24 hours post dosing. A further sample will be analyzed at the time point at which recrudescence/re-infection occurs (if applicable).
- q Single local ECG reading for inclusion purpose and triplicate central ECG reading for safety evaluation during study.
- h Laboratory safety will be performed locally: hematology, clinical chemistry, and urinalysis (see Appendix 2 for details).

Clinical Trial Protocol ACT14655 – artefenomel/ferroquine 13-Nov-2017 Version number: 1

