1.6 STATISTICAL MODIFICATIONS MADE IN THE STATISTICAL ANALYSIS PLAN

The primary efficacy population will be the PK/PD population instead of the mITT population stated in the protocol.

A per-protocol [PP] population was added in order to align the analysis population with the primary endpoint of the study. All populations have been further clarified from the protocol definitions

The derivation of the secondary endpoint, Fever clearance time (FCT), has been added. FCT will be assessed by measuring the time from the first dose until the first time that the body temperature dropped and remained <37.5 °C.

Time to 50% parasite reduction (T_{PC50}) will also be calculated in addition to the time to 99% PR.

The evaluation of the relationship between parasitemia (as measured on thick blood film and/or by qPCR) and concentration of OZ439/FQ may be performed in a separate analysis pooling data from different studies and be reported in a separate report.

The terminal half-life ($t_{1/2}$) for OZ439 and ferroquine will not be estimated as this endpoint does not contribute to the objectives of the study.

The definition of baseline to be used for efficacy analyses has been clarified.

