2.1.4.2.8 Fever clearance time (FCT)

FCT is the time from start of study drug administration until temperature remained below 37.5°C.

Fever is defined by a body temperature $\geq 37.5^{\circ}\text{C}$ for axillary temperature or by a body temperature $\geq 38^{\circ}\text{C}$ for other routes of measurement.

Timing to consider rules will be similar to what it is described in [Section 2.1.4.2.3](#). The FCT is the post-dose timing associated to the first vital sign assessment as defined above.

In case the FCT is not observed or confirmed before withdrawn (for any reason) or before start of rescue therapy, then the FCT will be censored at the time of the last vital sign assessment (using the post-dose timing above defined) before withdrawn or rescue therapy start, whichever comes first.

FCT is not applicable for patients with baseline body temperature $< 37.5^{\circ}\text{C}$ for axillary temperature (or $< 38^{\circ}\text{C}$ for other routes of measurement) or missing.

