2.4.4.2.6 Time to parasite clearance

Time to parasite clearance will be analysed using two endpoints:

- Time to confirmed parasite clearance
- Time to parasite clearance (with or without confirmation)

Descriptive statistics (such as median, 25% and 75% percentiles, minimum, and maximum) for each endpoint will be provided for each treatment arm.

2.4.4.2.6.1 Kaplan-Meier method

The time to each parasite clearance endpoint will be estimated by the failure function, $F(t)=P(T \leq t)$, probability that a patient will have parasite clearance before or at time t , using Kaplan-Meier method. The Kaplan-Meier (product-limit) estimate of the failure function for each group will be plotted on a same graph.

Cumulative number of events i.e. parasite clearances - and censures, in addition to quartiles of the survival times with their 95% confidence interval will be provided by treatment arm, and overall. Percentage will be based on the number of patients included in the analysis.

The model will run by using the SAS LIFETEST or ICLIFETEST procedures in order to compute and plot the estimate of the distribution of the survival time.

At $t=$ Hour 24, Hour 48, Hour 72, the number of patients at risk just prior t , the number of events and censures, and the probability that the time to parasite clearance exceeds t , with its 95% confidence interval, will be provided by treatment arm, and overall.

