2.4.4.2.11 Time to fever clearance

Same analyses than those described in [Section 2.4.4.2.6](#) for time to parasite clearance.

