- e Local thick and thin blood films performed at the site, before Informed Consent signature, according to local standard procedures and within 4 hours prior to dosing, can be used as screening/ pre-dose parasitemia assessments ([Section 9.1.1.1](#) of protocol) provided that a standard procedure is in place at site and blood films staining is performed according to the study operational manual. Blood films (thick and thin) and temperature measurements need to be confirmed as follows: when 1st parasite clearance and 1st temperature < 37.5 °C, measurements need to be confirmed with second reading 6 to 12 hours after the first measurement (ie, to determine Parasite Clearance and Fever Clearance). The first measurement (if confirmed) will be considered the 'Clearance Time'. Asexual and sexual counts will be measured separately: only asexual count will be used as parasitemia for evaluation of study endpoints. If parasites have not cleared within 72 hours after IMP administration and criteria for rescue medication are not met at 72 hours post-dose, blood films should continue to be taken according to site standard practice (or at minimum every 8 hours) until parasite clearance is shown or until criteria for rescue medication are met (see [Section 7.7.1](#) of protocol). If these additional blood smears are taken they should be recorded as unscheduled visits in the e-CRF. Axillary temperature should be recorded, if the axillary method is not possible, an alternative route (oral, tympanic, rectal) may be used. Within an individual participant the same method of temperature measure should be used throughout the study.
- f RT-qPCR and qPCR will be performed at all parasitemia time-points (To be collected, according to the schedule and the instructions reported in the study operational manual). Parasite genotyping analysis will be performed on previously collected blood spot sample only in case of a positive blood film after initial parasite clearance: one pre-dose sample and one sample at 18 or 24 hours post dosing. A further sample will be analyzed at the time point at which recrudescence/re-infection occurs (if applicable).
- g Single local ECG reading for inclusion purpose and triplicate central ECG reading for safety evaluation during study.
- h Laboratory safety will be performed locally: hematology, clinical chemistry, and urinalysis (see [Appendix 2](#) of protocol for details).

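### Fever clearance time has two rules: SAP 1.6 and 2.1.4.2.8 require temperature to stay below 37.5 °C with no window, while schedule footnote e accepts a first reading confirmed 6 to 12 hours later

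*SAP*

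**What the plan says.** Fever clearance time (FCT) is a secondary endpoint added by the SAP. SAP 1.6 counts from first dose "until the first time that the body temperature dropped and remained <37.5 °C". SAP 2.1.4.2.8 repeats the idea: "FCT is the time from start of study drug administration until temperature remained below 37.5°C". Neither sentence says for how long.

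Footnote e, the same in the protocol schedule and SAP Appendix A, has a bounded rule. Once a temperature below 37.5 °C has been read for the first time, "measurements need to be confirmed with second reading 6 to 12 hours after the first measurement (ie, to determine Parasite Clearance and Fever Clearance"). It then fixes the date: "The first measurement (if confirmed) will be considered the 'Clearance Time'".

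Three other places bear on the reading:

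- **Censoring (SAP 2.1.4.2.8).** The rule begins "In case the FCT is not observed or confirmed before withdrawn (for any reason) or before start of rescue therapy", and then censors at the last vital sign assessment before withdrawal or rescue. *Confirmed* is not defined there.
- **Cross-reference (SAP 2.1.4.2.8).** The section borrows the timing rules of 2.1.4.2.3 (parasite clearance). In 2.1.4.2.3 the 6 to 12 hour confirmation rule stands under a different subheading from the timing rules.
- **Analysis (SAP 2.4.4.2.11).** FCT is analysed like time to parasite clearance. That has a confirmed version and a second one, "Time to parasite clearance (with or without confirmation)".

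SAP 2.1.4.2.8 defines fever as 37.5 °C or above by the axillary route and 38 °C or above by other routes. Its clearance threshold is 37.5 °C whatever the route.

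**The concern.** FCT should measure how fast the presenting fever resolves. Temperature is scheduled at every visit to Day 28, so a rule that requires it to stay low without limit also measures freedom from later febrile recurrence, which has its own endpoints in SAP 2.1.4.2.4 to 2.1.4.2.6.

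Recurrence is part of treatment failure, and the planning model expects failure to fall steeply with OZ439 dose. Under the literal rule, early clearances would be lost mostly in the FQ-alone arm, and the FCT curves could separate by dose even if OZ439 did nothing to fever. A programmer working from 2.1.4.2.8 alone would find no window there and no pointer to footnote e.

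**Working it through.** **1. The two rules on one hypothetical participant.** Baseline is 38.6 °C and readings are below 37.5 °C from Hour 12. On Day 21 there is parasitemia with 37.9 °C (late clinical failure), and rescue is given.

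- Footnote e: FCT = 12 h.
- Literal SAP sentence: temperature did not remain below 37.5 °C before rescue, so FCT is censored at Day 21 (21 × 24 = 504 h).

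A second participant has the same early course, one unrelated reading of 37.6 °C on Day 14, and no fever afterwards. Footnote e gives 12 h. The literal sentence gives the next scheduled reading, Day 21.

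**2. Inputs.** The plan states no figure for FCT, so there is none to reproduce.

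- From protocol Appendix 8 and SAP 1.3: expected Day 28 PCR-corrected ACPR of 72/81/91/97% at OZ439 0/300/600/1000 mg. Failures are 100% minus these: 28/19/9/3%.
- Assumed: the share *f* of failures that are late febrile recurrences (25% or 50%), and 15 or 30 participants per arm febrile at baseline.
- Assumed: one true FCT distribution for all arms, with 10, 15, 15, 20, 12, 10, 12 and 6% clearing at 6, 12, 18, 24, 30, 36, 48 and 72 h.

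**3. Apparent proportion cleared by 72 h, literal rule** = 1 − *f* × failure rate. The true value is 100% in every arm.

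| OZ439 dose | *f* = 25% | *f* = 50% |
|---|---|---|
| 0 mg | 1 − 0.25 × 0.28 = 93.0% | 1 − 0.50 × 0.28 = 86.0% |
| 300 mg | 95.3% | 90.5% |
| 600 mg | 97.8% | 95.5% |
| 1000 mg | 99.3% | 98.5% |

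**4. Median.** By 24 h, 10 + 15 + 15 + 20 = 60% have truly cleared. In the worst arm at *f* = 50%, 0.86 × 60% = 51.6%, still above half, so the median stays at 24 h in all arms. The upper quartile does move. By 36 h, 82% have truly cleared, and 0.86 × 82% = 70.5% falls short of 75%. The FQ-alone quartile therefore shifts from 36 h to 48 h, as does that of the 300 mg arm (0.905 × 82% = 74.2%).

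**5. False dose trend.** The simulation used 3,000 trials per scenario, identical true FCT in all arms, and recurrences censored at Day 14, 21 or 28. The test was a Cox-type score test on OZ439 dose, two-sided 5%.

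| Rule | 15 febrile per arm | 30 febrile per arm |
|---|---|---|
| Footnote e | 5.5% | 5.3% |
| Literal, *f* = 25% | 8.7% | 12.4% |
| Literal, *f* = 50% | 16.4% | 29.6% |
| Literal, unrelated fever only, 5% of every arm | 5.0% | 4.5% |
| Literal, unrelated fever only, 10% of every arm | 5.1% | 5.1% |

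**6. Route.** A tympanic reading of 37.7 °C is below the 38 °C fever definition but not below 37.5 °C, so it is neither fever nor clearance.

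**The case against.** The strongest reply is that the documents already bound the period. Footnote e names fever clearance expressly and is part of the SAP. The censoring rule speaks of FCT being confirmed, and the only fever confirmation rule anywhere is the 6 to 12 hour one. SAP 1.6 says *the first time*. A later fever cannot alter the version analysed with or without confirmation. This stands as evidence of what was probably intended. It does not settle the derivation, because 2.1.4.2.8 neither states the window nor cites footnote e, and it imports only timing rules.

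The size is also open to challenge:

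- The failure rates include early failures, which are not late recurrences, and late parasitological failures, which are afebrile by definition. The febrile share is in neither document.
- FCT applies only to participants febrile at baseline, while inclusion criterion I 02 also accepts documented history of fever. Thirty per arm is therefore a ceiling: every evaluable participant.
- The SAP text plans descriptive and Kaplan-Meier output for FCT. A Cox model for it appears only in the summary table at the end of Appendix B. That table also names the PP population where SAP 2.4.4.2 uses mITT for this endpoint.

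These points stand, and they make the percentages illustrative.

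A reader might infer that the plan contains no limit at all, or that any later fever creates a false dose effect. Footnote e rules out the first. For the second, nothing in the documents suggests that unrelated fever differs by arm. Step 5 shows that it adds noise, with rejection staying near 5%.

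**Conclusion.** The plan is internally inconsistent on FCT, and the two rules give different values for the same participant. If the SAP sentence is programmed literally, late febrile recurrence turns early clearances into censored values, mostly in the FQ-alone arm. At an assumed 50% febrile share, apparent clearance by 72 h is 86/91/96/99%. For shares of 25 to 50% and 15 to 30 baseline-febrile participants per arm, all assumed, a dose-trend test rejects falsely in about 9 to 30% of trials. Median FCT hardly moves under the assumed distribution.

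It would go too far to say that the plan as a whole commits to the unbounded rule or will produce a false OZ439 effect: a bounded rule exists and other wording leans towards it. FCT is a secondary endpoint with no multiplicity control, and the primary analysis and sample size are unaffected. It should be corrected before the endpoint is programmed.

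**What to change.** In SAP 1.6 and 2.1.4.2.8, replace the *remained* wording with one definition:

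- FCT is the assigned post-dose time point of the first temperature below the fever threshold for the route used (37.5 °C axillary, 38 °C other routes, as 2.1.4.2.8 already defines fever). It must be confirmed by a reading 6 to 12 h later that is also below that threshold, or by the next available reading if none falls in that interval.
- Fever after confirmed clearance does not change FCT.
- Participants without confirmed clearance before rescue or withdrawal are censored as now.
- Intervals are taken from assigned time points. SAP 2.5.4.1 collects only the date of temperature, so before Day 4 the time point comes from the accompanying blood film, or from the visit's nominal time if there is no film.

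The next-available clause is needed because scheduled films go from 48 h to 72 h, beyond the confirmation interval unless an extra reading is taken. State in SAP 1.6 that the route-specific threshold extends footnote e, which uses 37.5 °C for all routes. The cost is one definition and its programming; no new data are needed.

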2.1.4.2.9 Parasite Reduction Ratio (PRR)

Observed Parasite Reduction Ratio (PRR) will be provided at 24 h, 48 h, and 72 h.

The observed PRR_t (where t takes the following values 24h, 48h and 72h after IMP administration) is defined as the ratio of the number of parasites P_0 at time $t=0$ (before treatment) divided by the parasite count P_t at time t (post-treatment).

$$\text{PRR}_t = P_0/P_t$$

When calculating the observed parasite reduction ratio, if the post dose parasite count is equal to 0 (due to a negative parasitemia) then a value of 1 parasite/ μ L will be imputed to allow a parasite reduction ratio to be calculated.

2.1.4.2.10 Parasite Clearance Rate

Parasite clearance estimator according to worldwide antimalarial resistance network WWARN will be used to identify the lag phase, tail, clean the data for outliers, and determine the best model (linear, quadratic, cuboidal) to fit the log-transformed parasite data and afterward calculate the following estimate: the parasite clearance rate. The **parasite clearance rate “k”** will be defined as the minus slope of the natural logarithm parasitemia versus time linear relationship, after exclusion of outliers, lag phase and tail, using the WWARN Parasite Clearance Estimator (PCE) method developed by Flegg et al. (2011) (1) through the calculate PCE function of the bhrcc R Software Package.

Outliers are defined as parasite counts which are not biologically possible or are highly unlikely based on other parasite measurements in the same individual.

Lag phase is defined as the initial part of the parasite clearance profile which has a much flatter slope than the remaining part of the profile. It is important to note that a lag phase is not observed in all profiles.

Tail is defined as terminal part of the parasite clearance profile when parasitaemia remains close to the detection limit and does not decrease over a number of measurements time-points. Tails are not observed in all profiles.

Two other methods for estimating parasite clearance rate (k) could be explored if deemed useful or if the first method detailed above could not be used:

- A Tobit regression model (SAS proc Lifereg) will be used in order to take into account for censored observations (i.e. negative parasitemia) however only the first zero sustained (i.e. followed by negative slides only) will be included in the analysis. In addition, a linear regression model starting from the second parasite measurement will be fitted if this second measurement exceeded the first measurement (baseline) by more than 25%. The Tobit model is a censored regression model, where the response variable Y_i is related to a latent (or unobservable) variable Y^*_i by:

$$Y_i = Y^*_i \text{ if } Y^*_i > Y_L, Y_i = Y_L \text{ if } Y^*_i \leq Y_L.$$

The latent variable is then modelled in the standard way: $Y^*_i = X_i\beta + \varepsilon$. And the regression model is solved using maximum likelihood techniques, however the likelihood function is now a truncated normal distribution in the case when $Y^*_i \leq Y_L$.

- Using the Bayesian Hierarchical Regression model introduced in Fogarty et al. (2015) (2) through the ‘clearance Estimator Bayes’ function of the ‘bhrcc’ R Software Package. As the calculate PCE function , this function estimates parasite clearance rates, through a change point model on the log of the parasite densities to account for three potential phases: (1) a constant phase (the lag phase); (2) a phase with a linear decrease (decay phase); (3) another constant phase (the tail phase). Hence the estimation of the parasite clearance rate is only based on observations within the decay phase. In contrast to the

calculate PCE function, the Bayesian approach in the clearance Estimator Bayes function allows treating the delineation between lag, decay, and tail phases within an individual's clearance profile as being random variables, thus taking into account the additional uncertainty of boundaries between phases. The clearance Estimator Bayes function also allows taking account for covariates (such as laboratory for qPCR), while calculate PCE function does not.

Based on the linear model that is fitted to the linear part of the parasite clearance profile, the time taken for the parasitaemia to be reduced to 50% and 99% of the baseline parasitaemia (PC50 & PC99) will be estimated using the WWARN calculator.

2.1.4.2.11 Time to 50% and 99% parasite reduction

The estimated time in hours it takes for the parasitaemia to decrease by half (50%) and by 99%, independent of the baseline parasitaemia, will be derived. The estimated time to reductions are constants independent of the baseline parasitaemia since reduction in parasitaemia follows the first order process (after excluding tail and lag phase). The estimated time to reductions will be calculated using the below methodology:

The predicted PRR_t is defined as the ratio of the number of parasites P₀ at time t=0 (before treatment) divided by the parasitemia at time t using the following equation: P_t = P₀ e^{-kt} (where k is the first-order elimination rate constant).

$$\text{PRR}_t = P_0/P_t$$

P₀ / P_t = 1 / e^{-kt} → PRR_t = 1 / e^{-kt}. By using logarithmic transformation, the log-linear relationship between the parasite reduction ratio (PRR_t) and the **parasite clearance rate** (k [as defined in section 2.1.4.2.11]) is:

$$\text{Log}(\text{PRR}_t) = kt$$

Time to 50% parasite reduction: the time needed for parasitemia to be reduced by half (called parasite clearance half-life) can be calculated by the following formula:

$$T_{\text{PC50}} = \log(2)/k = 0.693/k \text{ where } k \text{ is the clearance rate constant.}$$

Time to 99% parasite reduction: The time needed for parasitemia to be reduced by 99% can be calculated by the following formula:

$$T_{\text{PC99}} = \log(100)/k = 4.605/k \text{ where } k \text{ is the clearance rate constant.}$$

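### T_PC99 and T_PC50 use a post-lag slope but count from a pre-treatment time zero, so they are too short for any patient with a lag phase

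*SAP*

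**What the plan says.** Protocol Section 4 (Table 1) lists time in hours to 99% parasite reduction as a secondary endpoint under the OZ439 dose-response objective. Protocol 10.3.1 (Table 8) analyses it by Kaplan-Meier and by a Cox model with OZ439 dose and baseline parasitemia.

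The SAP then gives the following:

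- **2.1.4.2.10.** k is minus the slope of log parasitemia on time, "after exclusion of outliers, lag phase and tail". The lag is the "initial part of the parasite clearance profile which has a much flatter slope than the remaining part of the profile". The section adds: "It is important to note that a lag phase is not observed in all profiles". It also plans PC50 and PC99 from the fitted line by the WWARN calculator, described as "the time taken for the parasitaemia to be reduced to 50% and 99% of the baseline parasitaemia".
- **2.1.4.2.11.** P0 is the count at t = 0, before treatment, and P_t = P0·e^(−kt). "The time needed for parasitemia to be reduced by 99% can be calculated by the following formula": T_PC99 = 4.605/k. T_PC50 is 0.693/k. The section notes that decline is first order once lag and tail are left out.
- **2.1.4.2.12.** Estimated PRR24, PRR48 and PRR72 are k·t/ln(10) in log10 units.
- **2.4.4.2.4 and 2.4.4.2.5.** PC50 and PC99 are summarised descriptively. T_PC50 and T_PC99 get a geometric mean with 95% CI from a linear fixed effect model.
- **Summary of statistical analyses (end of Appendix B).** Time to 50% and 99% reduction is listed under Kaplan-Meier and Cox.

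SAP 1.6 records the addition of T_PC50. It records no change of method for the 99% endpoint.

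**The concern.** The slope comes from the decay phase, but the clock starts before dosing. Combining the two assumes full-rate decline from time zero, which is untrue of a profile from which a lag had to be removed. The result carries the name of the protocol endpoint, which a reader will take as hours from dosing.

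The endpoint serves the objective of showing how OZ439 dose affects parasite clearance. If the lag differed between arms, T_PC99 could not show it, because the lag has been taken out. T_PC50, T_PC99 and the three estimated PRRs are all fixed functions of k, so none of them can bring it back.

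The SAP also holds two quantities for the same endpoint, PC99 and T_PC99. They can differ for one patient, and nothing says which is the protocol endpoint.

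**Working it through.** **1. The plan's own constants.** ln(100) = 4.605 and ln(2) = 0.693, so both reproduce. At t = 4.605/k the formula gives PRR = e^4.605 = 100. It is correct when decline at rate k starts at time zero.

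**2. With a lag.** Let the lag last L hours with slope k_L < k (the SAP's flatter initial slope). If 99% reduction is reached after the lag:

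time from dosing = L + (4.605 − k_L·L)/k = 4.605/k + L × (1 − k_L/k)

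The shortfall in T_PC99 is therefore L × (1 − k_L/k). It is positive for every lag that meets the SAP's definition and zero without a lag. The same expression holds for T_PC50 if the 50% point falls after the lag. If it falls inside a slowly declining lag, the time is 0.693/k_L, still longer than 0.693/k.

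**3. Size.** The documents give no k, lag length or lag frequency. I assume k from 0.10 to 0.30 per hour and lags of one or two film intervals (films are every 6 h to 36 h).

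| k (/h) | 4.605/k (h) | Flat 6 h lag: time from dosing (T_PC99 too short by) | Flat 12 h lag | 6 h lag, falling at k/2 |
|---|---|---|---|---|
| 0.10 | 46.1 | 52.1 (11.5%) | 58.1 (20.7%) | 49.1 (6.1%) |
| 0.15 | 30.7 | 36.7 (16.3%) | 42.7 (28.1%) | 33.7 (8.9%) |
| 0.20 | 23.0 | 29.0 (20.7%) | 35.0 (34.3%) | 26.0 (11.5%) |
| 0.30 | 15.4 | 21.4 (28.1%) | 27.4 (43.9%) | 18.4 (16.3%) |

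If parasitemia rises at 0.25k during a 6 h lag, the shortfall is 6 × 1.25 = 7.5 h.

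**4. Check on a profile.** A noise-free profile was built on the 0, 6, 12, 18, 24, 30, 36 and 48 h films, with k = 0.20 and a flat 6 h lag. Fitting after the lag returns k = 0.20 and T_PC99 = 23.0 h. The same fitted line reaches 1% of baseline at 29.0 h. A baseline-referenced reading of the line thus recovers the lag.

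**5. Estimated PRR.** For t beyond the lag, log10 PRR is too high by (k − k_L)·L/ln(10). With k = 0.20 and a flat 6 h lag this is 1.2/2.303 = 0.52 log10, a 3.3-fold overstatement at each of 24, 48 and 72 h. Observed PRR uses actual counts, so the two can disagree for one patient.

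**6. From patient to arm.** At k = 0.20, reported over true is 23.03/29.03 = 0.793. If a share f of an arm has that lag, the arm's geometric mean is multiplied by 0.793^f, from 1 at f = 0 to 0.793 at f = 1. The documents do not give f.

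**The case against.** **The definition is disclosed.** As the duration of a 99% fall within the decay phase, 4.605/k is right, and SAP 2.1.4.2.11 says lag and tail are excluded. That stands for the arithmetic. It does not cure the pre-treatment time origin or the use of the protocol endpoint's name.

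**A baseline-referenced PC99 is already planned.** This also stands, and it makes the fix cheap. What remains is that the CI and model go to T_PC99 and no endpoint is designated.

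**Stronger readings a reader might infer:**

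- *The trial would miss a lag effect of OZ439.* Not supported. Time to parasite clearance, observed PRR and parasitemia by time point and arm all keep the lag. Nothing in the documents says the lag differs by arm.
- *Every patient has a lag*, from the remark in SAP Table 1 that the drug has no activity in the first 24 h. That remark classifies early severe malaria as wrong inclusion and does not estimate a lag. SAP 2.1.4.2.10 says only some profiles show one.
- *Lag plus 4.605/k is the true time.* This is exact only for a flat lag. The SAP defines a flatter slope, not a zero one.
- *The SAP dropped the time-to-event analysis.* It did not do so cleanly: 2.4.4.2.5 omits it, but the summary table keeps Kaplan-Meier and Cox.

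**The fallback estimators differ.** The Bayesian model also excludes the lag. The optional Tobit fit describes no lag estimate and can leave lag points in. In a simple linear analogue (k = 0.20, flat 6 h lag), k fell to 0.185 and 4.605/k rose to 24.8 h, still below 29.0 h.

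**Conclusion.** The point holds as an error of time origin. For a patient with a lag, T_PC99 understates time from dosing by L × (1 − k_L/k), T_PC50 is also too short, and the estimated PRRs are too high. Patients without a lag are unaffected.

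Under the assumed flat 6 h lag and k of 0.10 to 0.30 per hour, the shortfall in T_PC99 is 11.5% to 28.1% for that patient. It is 6 h if the lag is flat, 3 h if parasitemia falls at half of k, and more than 6 h if it rises. These are illustrations, not estimates for this trial. They should not be read as the bias in an arm's geometric mean, which depends on an unknown share of patients with a lag.

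One protocol secondary endpoint is affected, together with quantities derived from the same k. The primary exposure-response analysis is not.

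**What to change.** Make these changes in the SAP before database lock:

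1. Name the WWARN calculator's PC99 as the protocol endpoint, with PC50 as its companion, and analyse these in 2.4.4.2.5. State that both are counted from dosing against baseline parasitemia. For PC50, say what applies when the 50% point falls within the lag, where the fitted line does not describe the data.
2. Relabel 0.693/k as decay-phase half-life and 4.605/k as decay-phase duration of a 99% fall. Label the estimated PRRs as decay-phase values too.
3. In 2.1.4.2.10, change reduced *to* into reduced *by*. Read literally, reduction to 99% of baseline is a 1% fall.
4. Reconcile 2.4.4.2.5 (linear model) with the summary table and protocol Table 8 (Kaplan-Meier and Cox). Record any departure from the protocol in SAP 1.6.
5. Report lag duration by arm.
6. Correct the cross-reference in 2.1.4.2.11: k is defined in 2.1.4.2.10.

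Do not substitute lag + ln(100)/k unless it is adjusted for any change in parasitemia during the lag.

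The cost is SAP wording and one small table. No new data are needed, and the main method already identifies the lag and plans PC50 and PC99. If the Tobit fallback were used, a rule for the lag would have to be added.
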